COVER LETTER

Statistical Analysis Plan

ORIGINAL TITEL:

Comparison between the caudal block and other methods of postoperative pain relief in children undergoing circumcision: A prospective randomized study

This study was approved by the research ethics committee operates Institution Review Board number 70130623

The study conforms to the provisions of the Declaration of Helsinki in 1995 (as revised in Edinburgh 2000) and it was ethically approved by the Research Committee for Government Hospitals, Salmaniya Medical Complex, Kingdom of Bahrain (IRB number: 70130623).

Data management

The collected data were recorded then presented and statistically analyzed by computer using SPSS 27.0 for Windows (*SPSS Inc., Chicago, IL, USA*) and Prism Graphpad version 9.4.1 (*Graphpad, San Diego, USA*). A test of normality was done using the Kolmogorov-Smirnov test. Kruskal-Wallis test was used to compare between groups for numerical variables, while Chi-square and Fisher's Exact test were used for categorical variables. Linear regression analysis was used to detect the predictors of pain scale. All tests were two-sided. The accepted level of significance in this work was ($p \leq 0.05$). A p -value ≤ 0.01 was considered highly statistically significant and $p > 0.05$ was considered non-statistically significant.

Results

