A total of 90 patients had participated in this current study. The study subjects were classified into 3 main groups. The first group (group A) received general anesthesia with caudal block including 29 patients. The second group (Group B) represented general anesthesia with an opioid group with a total of 33 participants, while the last group (Group C) was patients with a penile block 28 patients. Group B was significantly older in comparison with the other two groups, while Group A was the youngest age group as described in Table 1. No significant difference had been observed regarding operation duration among the three groups. Sevo Mac consumption is significantly lower in group A in comparison with the other two groups. Fentanyl consumption intra and post-operative is higher in group B followed by group C, while the lowest level of consumption with among group A patients. Participants' heart rates are shown in Figure 1. Group C significantly showed a higher mean heart rate intraoperative, 5, 10, 20, 30, and 60 minutes postoperative, while group B showed the lowest mean heart rate in the three groups ($p < 0.005$). The behavioral score is represented in figure 2 which had been measured 5, 10, 20, 30, and 60 minutes postoperative. Group C significantly demonstrated a higher percentage of severe discomfort in comparison with the other two groups in 5, 10, 20, and 30 minutes post-operative (82.1, 25.0%, 21.4%, and 3.6% respectively). The percentage of severe discomfort in group B in 5, 10, 20, and 30 minutes post-operative was 18.2, 6.1%, 3.0%, and 0.0% respectively, while only one patient expressed severe discomfort in 5, 10, and 20 minutes in group A. The pain scale was much higher among group C, while group A showed the lowest mean pain scale (Figure 3).

Table 2 represents the crying scale (5, 10, 20, 30, 60 minutes postoperative) among the studied groups. Group C showed a higher percentage of crying in comparison with the other two groups, however, the relation was non-significant.

The movement scale also was significantly different between the 3 groups in 5, 20, and 30 minutes post-operative (Table 3). Similarly, a significant difference was shown between the 3 groups in the agitation scale in 5, 10, and 30 minutes postoperative (Table 4). Table 5, demonstrated a

statistically significant difference between the 3 groups on the posture scale in 5, and 30 minutes post-operative.

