Table 6 explains that the type of block, fentanyl intraoperative and postoperative was the predictor of the 5-minute pain scale, while the type of block was only the significant predictor of the 10, 20, and 30-minute pain scale. The type of block and weight of participants were the predictors of the pain scale 60 minutes postoperative

Comparison between the caudal block and other methods of postoperative pain relief in children undergoing circumcision: A prospective randomized study

This study was approved by the research ethics committee operates Institution Review Board number 70130623

Table 1. Demographic data of children who underwent circumcision

Demographic data of children who underwent circumcision Variables	Group A (n=29) Mean±SD	Group B (n=33) Mean±SD	Group C (n=28) Mean±SD	P-value*	Significant pairs**
Age (months)	16.0±7.5	41.8±43.3	16.3±19.7	0.002	Group A vs.s Group B AND Group B vs Group C
Weight (KG)	10.3±2.4	11.3±3.8	9.0±5.1		0.130
Operation duration (minutes)	14.6±3.5	15.1±4.6	16.3±6.1		0.523
Sevo mac	0.5±0.3	2.0±1.6	1.5±0.2	<0.001	Group A vs. Group B AND Group A vs. Group C
Fentanyl intraoperative	9.9±5.4	22.1±9.1	16.4±5.4	<0.001	Group A vs Group B Group A vs. Group C AND Group B vs. Group C
Fentanyl postoperative	4.8±3.1	10.5±4.6	5.2±2.5	<0.001	Group A vs. Group B AND Group B vs. Group C

Comparison between the caudal block and other methods of postoperative pain relief in children undergoing circumcision: A prospective randomized study

This study was approved by the research ethics committee operates Institution Review Board number 70130623

Table 2:

represents the crying scale (5, 10, 20, 30, 60 minutes postoperative) among the studied groups. Group C showed a higher percentage of crying in comparison with the other two groups, however, the relation was non-significant

Crying scale (5, 10, 20, 30, 60 minutes postoperative) among studied groups

Brief title: Participants' Crying Scale

[figure not shown]
Variables	Group A (n=29) N (%)	Group B (n=33) N (%)	Group C (n=28) N (%)	P -value
5 minutes postoperative				
Not crying	19 (65.5)	19 (57.6)	13 (46.4)	0.344
Crying but responds to tender Loving care	10 (34.5)	14 (42.4)	15 (53.6)	
10 minutes postoperative				
Not crying	15 (51.7)	17 (51.5)	10 (35.7)	0.375
Crying but responds to tender Loving care	14 (48.3)	16 (48.5)	18 (64.3)	
20 minutes postoperative				
Not crying	19 (65.5)	16 (48.5)	12 (42.9)	0.200
Crying but responds to tender Loving care	10 (34.5)	17 (51.5)	16 (57.1)	

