30 minutes postoperative				
Not crying	13 (44.8)	15 (45.5)	14 (50.0)	0.912
Crying but responds to tender Loving care	16 (55.2)	18 (54.5)	14 (50.0)	

60 minutes postoperative

[figure not shown]
Not crying	17 (58.6)	19 (57.6)	12 (42.9)	0.407
Crying but responds to tender Loving care	12 (41.4)	14 (42.4)	16 (57.1)	

The comparison between groups was done using Chi square test (χ^2)

[figure not shown]
5 Minutes

10 Minutes

[figure not shown]

20 Minutes

[figure not shown]

- Relaxed and comfortable
- Mild discomfort
- Moderate pain
- Severe discomfort/pain

30 Minutes

60 Minutes

Behavioral score among studied groups. *Fisher's exact test was used* FLACC scores from 0-10 , zero is analgesia, 1-3 is for mild pain, 4-6 is for moderate pain, and 7-10 is for severe pain

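### The SAP calls severe discomfort significantly higher in Group C at 30 minutes, but this is one child of 28 against none of 33 in Group B (Fisher p = 0.46)

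*SAP*

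**What the plan says.** The SAP Results, on the behavioral score, say that "Group C significantly demonstrated a higher percentage of severe discomfort in comparison with the other two groups in 5, 10, 20, and 30 minutes" after surgery, and give Group C as 82.1%, 25.0%, 21.4% and 3.6%. For the comparators they say: "The percentage of severe discomfort in group B in 5, 10, 20, and 30 minutes post-operative was 18.2, 6.1%, 3.0%, and 0.0% respectively", and "only one patient expressed severe discomfort in 5, 10, and 20 minutes in group A". The group sizes are 29 (A), 33 (B) and 28 (C).

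The Data management section makes all tests two-sided and sets significance at p ≤ 0.05; anything above 0.05 "was considered non-statistically significant". The behavioral score figure has four categories, the last being "Severe discomfort/pain", and its note says "Fisher's exact test was used". The available text gives no p-value for this score at any time point and does not say whether the test used all four categories or severe against not severe.

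**The concern.** The sentence ties significance to one category (severe), to a comparison with both other groups, and to four named time points. At 30 minutes the Group C percentage is so small that it must be a single child, and a single event in groups of about 30 cannot reach p ≤ 0.05. A reader would nevertheless take an excess of severe discomfort half an hour after a penile block as shown. The other 30-minute results (movement, agitation, posture, regression) and the study's conclusion do not depend on this sentence.

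**Working it through.** **Inputs.** All are from the SAP Results. Each printed percentage for Groups B and C fits exactly one whole number of children. Group A is read as one child at each of 5, 10 and 20 minutes. Its 30-minute count is not printed and is inferred as 0 because its severe case is reported only for the earlier times.

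| Minutes | A (n=29) | B (n=33) | C (n=28) |
|---|---|---|---|
| 5 | 1 | 6 (18.2%) | 23 (82.1%) |
| 10 | 1 | 2 (6.1%) | 7 (25.0%) |
| 20 | 1 | 1 (3.0%) | 6 (21.4%) |
| 30 | 0 (inferred) | 0 (0.0%) | 1 (3.6%) |

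The printed figures reproduce: 1/28 = 3.6% and 0/33 = 0.0%. As a check on the group sizes, all five crying p-values in SAP Table 2 (0.344, 0.375, 0.200, 0.912, 0.407) also reproduce by Pearson chi-square.

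**30 minutes, C against B (printed figures only).** With one event among 28 + 33 = 61 children, the chance that it falls in Group C is 28/61 = 0.459, and in Group B 33/61 = 0.541. The two-sided Fisher p sums the outcomes no more probable than the one observed, so p = 0.459. Chi-square gives 0.274 uncorrected and 0.934 corrected. The difference is 3.6 percentage points (Newcombe 95% CI -7.3 to 17.7).

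**30 minutes with A at the inferred 0/29.** C against A: 28/57 = 0.491, difference 3.6 points (-8.5 to 17.7). Three-group exact test: 28/90 = 0.311.

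**If A at 30 minutes were not 0.**

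| Severe cases in A | A, % | Three-group exact p |
|---|---|---|
| 1 | 3.4 | 0.53 |
| 2 | 6.9 | 0.30 |
| 3 | 10.3 | 0.11 |
| 4 | 13.8 | 0.039 |

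With one case, A and C are almost equal (3.4% against 3.6%; pairwise p = 1.00). From two cases on, A is the higher group, so the sentence would be wrong in direction before the test reached 0.05. C against B stays at 0.459 throughout.

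**What Group C would have needed.** For k severe cases in C and none in B, p = C(28,k)/C(61,k) at the values shown: k = 3 gives 3276/35990 = 0.091 and k = 4 gives 20475/521855 = 0.039. Against A at 0/29, k = 4 gives 0.052 and k = 5 gives 0.023. Group C had one.

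**The other time points, if the table was severe against not severe.**

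| Minutes | C vs A | C vs B | Three-group p | Holm over four times |
|---|---|---|---|---|
| 5 | 4.0e-10 | 5.9e-7 | 3.3e-11 | 1.3e-10 |
| 10 | 0.025 | 0.067 | 0.030 | 0.075 |
| 20 | 0.052 | 0.041 | 0.025 | 0.075 |
| 30 | 0.491 | 0.459 | 0.311 | 0.311 |

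Only at 5 minutes is C separated from each comparator by pairwise Fisher.

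**Could a four-category test settle it?** Two assumed 30-minute tables (relaxed/mild/moderate/severe), both with severe fixed at 0, 0 and 1, show the range:
- A 20/7/2/0, B 23/8/2/0, C 19/6/2/1: overall exact p = 0.99.
- A 24/4/1/0, B 24/7/2/0, C 12/10/5/1: p = 0.031, and 0.019 if the one severe child is recoded as moderate.

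An overall test can go either way. In the significant example the result does not come from the severe category.

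**The case against.** The strongest reply is that this is loose phrasing and not a wrong calculation. Every printed percentage is right, no visible p-value is wrong, and the figure suggests one Fisher test per time point on all four categories, with the severe percentages quoted as description. The heart-rate sentence in the same section has a similar shape and a single shared p-value. If that is what was done, the test result may be valid and only the sentence needs repair. That stands as a possible source of the word, but it does not support the claim as written. For the movement scale the SAP uses overall wording: "The movement scale also was significantly different between the 3 groups in 5, 20, and 30 minutes post-operative (Table 3"). The behavioral sentence instead names the severe category and both comparators.

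The points at 10 and 20 minutes are weaker, and this also stands. They apply only if severe against not severe was tested, and only if each comparator is meant separately. Group C against A and B combined gives p = 0.009 at 10 minutes and 0.010 at 20, and the three-group values meet the SAP's threshold. The SAP specifies no multiplicity adjustment. The Holm family used here is the four times the sentence claims, although the score was measured at five. None of this helps at 30 minutes, where C against A and B combined gives 0.311.

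It is also fair that the percentages and group sizes are printed, so a careful reader can find the single child. That limits the harm but does not make the statement correct.

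**Conclusion.** The concern holds and is minor. On printed figures alone, severe discomfort at 30 minutes is 1/28 in Group C against 0/33 in Group B, p = 0.46, and the SAP's own rule calls that non-significant. The comparison with Group A (p = 0.49) and the three-group result (p = 0.31) rest on the inferred 0/29, but the conclusion does not. Whether the four-category score differed overall at 30 minutes cannot be judged from the available text and is not disputed. At 10 and 20 minutes the wording is doubtful only against each comparator separately, and only if the tested table was severe against not severe.

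**What to change.** Remove *significantly* for severe discomfort at 30 minutes and report one child in Group C, not significant. Confirm the Group A count if the figure does not show it. State which table Fisher's test used, and word every time point to match:

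- **All four categories:** say that the behavioral score differed between the three groups at the times where that test gave p ≤ 0.05, and give the severe percentages as description only.
- **Severe against not severe:** give the three-group p-values (<0.0001, 0.030, 0.025, 0.31), say that they are unadjusted for four time points, and do not claim a difference from each comparator at 10 or 20 minutes.

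A separate small correction concerns the Results text and the Table 2 caption, which say "Group C showed a higher percentage of crying in comparison with the other two groups, however, the relation was non-significant". Group C was higher at 5, 10, 20 and 60 minutes but lower at 30 (14/28 = 50.0%, against 16/29 = 55.2% in A and 18/33 = 54.5% in B). Pooled over the five times it is still highest (79/140 = 56.4%, against 62/145 = 42.8% and 79/165 = 47.9%), so the sentence needs only a qualifier.

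The cost is a text edit and one sentence naming the tested table, with no new data and no change to any stated conclusion.

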Cover letter

Study protocol

ORIGINAL TITEL:

Comparison between the caudal block and other methods of postoperative pain relief in children undergoing circumcision: A prospective randomized study

Institution review board number (IRB number: 70130623).

Approval date 13\06\2023

The study conforms to the provisions of the Declaration of Helsinki in 1995 (as revised in Edinburgh 2000) and it was ethically approved by the Research Committee for Government Hospitals, Salmaniya Medical Complex, Kingdom of Bahrain (IRB number: 70130623).

Selecting the best analgesia method in pediatrics is so important. This is a randomized a prospective study conducted on 90 children who underwent circumcision. The results showed that circumcision in pediatrics using a caudal block can provide longer analgesia for the patient.

ABSTRACT

Background:

Caudal block (CB), dorsal nerve penile block (DPNB), and systemic opioids are common techniques used in pediatric surgeries to provide analgesia for penile surgery such as circumcision.

Aims: This study aimed to compare the effectiveness of the CB with other methods of postoperative pain release.

Material and Methods: The main operation pediatric theater and post-anesthesia recovery unit (PACU) in the Government Hospitals, Salmaniya Medical Complex, Bahrain.

Study subjects: Successive children aged 3 months to 3 years who had American Society of Anesthesiologists with Physical Status classification one and who had undergone elective circumcision

surgery were recruited., Children were randomized to one of three modalities of intraoperative analgesia: CB, or DPNB. And systemic opioids.

study design: Prospective, Observation-randomized, case-controlled trial study. a study Sample size: all patients, for a total of 90 boys going for circumcision surgery. I was recruited over the course of four months, starting in May 2023. The patients will be divided into three groups: A (CB), B systemic opioids, and C (DPsNB). All patients had operations and were observed, and the three groups were compared based on hemodynamic stability, pain scores, duration of sedation,

analgesia need, and parental satisfaction. where the Face, Leg, Activity, and Cry Consolability s(FLACC) pain scale and behaviors were used to observe and compare the three Groups.

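### The pain regression lists post-allocation, arm-dependent fentanyl beside type of block, leaving unclear what either result estimates

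*SAP*

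**What the plan says.** The SAP's Data management section gives one sentence on the model: "Linear regression analysis was used to detect the predictors of pain scale". It does not state which covariates entered, whether they were fitted together or one at a time, how the three-level block variable was coded, or what the coefficients are meant to estimate. For group comparisons it says "Kruskal-Wallis test was used to compare between groups for numerical variables", with Chi-square and Fisher's exact tests for categorical variables. None of these adjusts for anything.

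The Results then report, for 5 minutes: "Table 6 explains that the type of block, fentanyl intraoperative and postoperative was the predictor of the 5-minute pain scale". For 10, 20 and 30 minutes only type of block is named as significant. For 60 minutes: "The type of block and weight of participants were the predictors of the pain scale 60 minutes postoperative".

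The Protocol abstract randomises children to a modality of intraoperative analgesia, one of which is systemic opioids. Its list of comparisons includes "analgesia need, and parental satisfaction". The SAP Results add "Fentanyl consumption intra and post-operative is higher in group B followed by group C" and "Group B was significantly older in comparison with the other two groups".

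**The concern.** Fentanyl given during and after surgery comes after randomisation. It is not a baseline characteristic. In group B it may be part of the allocated treatment (the documents do not name that arm's opioid), and analgesia need is itself an outcome to be compared. Placing it beside type of block in a list of predictors treats a possible consequence of the arm as if it stood on the same footing as the arm.

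What is at stake depends on the model. In a joint model, the block coefficient compares children in different arms who received equal fentanyl, which is a different question from the total effect of allocation. In a univariable model, fentanyl carries the arm differences in pain with it.

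There is also a timing problem for postoperative fentanyl. Nothing in the documents places it before the 5-minute score, so it may have been given afterwards or because of the pain that was scored.

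The regression matters because it is the only named method that can adjust for baseline differences, and group B is about 26 months older on average than A and C.

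**Working it through.** **Inputs.** SAP Table 1, n = 29 (A), 33 (B), 28 (C); the fentanyl unit is not stated.

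| | A | B | C |
|---|---|---|---|
| Intraoperative fentanyl | 9.9±5.4 | 22.1±9.1 | 16.4±5.4 |
| Postoperative fentanyl | 4.8±3.1 | 10.5±4.6 | 5.2±2.5 |
| Age, months | 16.0±7.5 | 41.8±43.3 | 16.3±19.7 |

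**1. Reproducing Table 1.** Kruskal-Wallis needs individual data, so one-way ANOVA from the summary figures stands in. SS between = Σn(mean − grand mean)²; SS within = Σ(n−1)SD²; eta² = SS between / (SS between + SS within).

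- Intraoperative: grand mean 1475.6/90 = 16.40; SS between 2297.4; SS within 4253.7; F(2,87) = (2297.4/2)/(4253.7/87) = 23.5; eta² = 2297.4/6551.1 = 0.351.
- Postoperative: grand mean 631.3/90 = 7.01; SS between 635.3; SS within 1114.9; F(2,87) = 24.8; eta² = 635.3/1750.2 = 0.363.

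Both p-values are far below 0.001, as Table 1 reports. Welch tests agree with its listed pairs: all three differ intraoperatively (p = 3e-8 for A-B, 3e-5 for A-C, 0.004 for B-C). Postoperatively A-B and B-C differ, and A-C does not (p = 0.59). The SDs differ between arms, so eta² is descriptive only.

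**2. Where the arm dependence lies.** The A-versus-C part of SS between is (29×28/57)(difference)².

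- Intraoperative: 14.25×6.5² = 601.9, or 26.2%; the other 73.8% is B against A and C.
- Postoperative: 14.25×0.4² = 2.3, or 0.4%; the other 99.6% is B against A and C.

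Welch 95% intervals: A−B is −12.2 (−16.0 to −8.4) intraoperatively and −5.7 (−7.7 to −3.7) postoperatively. C−A is 6.5 (3.6 to 9.4) and 0.4 (−1.1 to 1.9). Postoperative fentanyl therefore overlaps mainly with contrasts against B, and intraoperative fentanyl with all three.

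**3. If fitted jointly.** With block as a categorical factor and no other covariates, least squares gives

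total contrast = adjusted contrast + b_intra × (difference in mean intraoperative fentanyl) + b_post × (difference in mean postoperative fentanyl).

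For B−A the added part is 12.2·b_intra + 5.7·b_post. The slopes are not available, so this cannot be evaluated. Purely as an assumption, slopes of the same sign and 0.05 to 0.10 pain points per unit would separate the two contrasts by 0.90 to 1.79 points (B−A), 0.35 to 0.69 (C−A) and 0.55 to 1.10 (C−B). With opposite signs of 0.05 the B−A gap would be 0.61 − 0.285 = 0.325. With zero slopes there is no gap. The identity does not depend on whether fentanyl is significant, only on its being in the model.

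**4. If fitted one at a time.** Suppose fentanyl has no effect on pain within any arm. The univariable slope is then between-arm Sxy / total Sxx. The Results say only that pain was highest in C and lowest in A, so the arm means here are assumed.

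- Pain means 1, 2, 7 (A, B, C): postoperative slope = −189.8/1750.2 = −0.108.
- Pain means 1, 4, 6: postoperative slope = 91.1/1750.2 = +0.052.

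Arm differences alone produce a slope and can reverse its sign. Across all the patterns tried, with within-arm SD 1.5 to 2.5, intraoperative slopes ran from +0.03 to +0.09 (p from 0.005 to 0.55) and postoperative slopes from −0.14 to +0.05 (p from 0.09 to 0.61). These illustrate the mechanism and do not estimate what happened.

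**5. Age, before it is used as a covariate.** B−A is 25.8 months and B−C 25.5. The Protocol recruits from 3 months to 3 years. Group B's mean of 41.8 months lies above 36. Its SD is also too large for that range: values between 3 and 36 months cannot have an SD much above half the range, 33/2 = 16.5, and group C's 19.7 exceeds this too. The age data need checking first.

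**The case against.** The strongest reply is that the SAP uses the regression only to search for predictors. It makes no causal claim and nowhere presents a coefficient as the randomised block effect. An association search may list correlated variables, and confounding by arm is an objection only to a causal reading. Table 6 cannot be seen, so no wrong number has been shown. The group comparisons stand by themselves, including severe discomfort at 5 minutes (82.1% in C, 18.2% in B, one of 29 in A), and the plan never promised a baseline-adjusted effect.

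Most of this stands. It limits the point to what the regression results can be used for, and it lowers the severity. It does not remove the point, because under either model form part of the 5-minute statement cannot be taken at face value, and a clearer analysis needs only data already collected.

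Three stronger readings might be inferred, and the documents do not support them:

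- That the block effect is known to be biased. No coefficient is available, and zero within-arm slopes would mean no distortion in expectation.
- That the problem is confined to 5 minutes. The wording for 10 to 30 minutes suggests that other variables were tested there. A non-significant fentanyl term would still change what the block coefficient means.
- That univariable models would leave the block result safe. If block was entered as a single numeric code, its coefficient is a linear trend across codes, not a set of arm contrasts.

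**Conclusion.** The point holds, at minor to moderate severity. Two post-allocation variables that depend strongly on arm are reported as predictors of pain beside the randomised factor, without a stated model form, coding or estimand.

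The arm dependence is well supported: about 35% of the variance of each fentanyl variable, driven almost wholly by group B for the postoperative amount. The consequence for the block and fentanyl results is conditional on how the models were fitted, and its size and direction are unknown. The conclusion rests on Table 1 being correct and on fentanyl following allocation, which the randomised comparison of analgesic modalities implies. The unadjusted between-group tests are not called into question by this point.

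**What to change.** - Estimate the block effect on pain at each time point from a regression with arm as two indicators plus baseline covariates only, without fentanyl. Age and weight qualify because they are baseline values already collected; weight should not be chosen because it was significant at 60 minutes.
- Check the age data against the recruitment limit first. Then report the model with and without age, because the Table 1 summaries suggest poor overlap between arms (16.0±7.5 in A, 41.8±43.3 in B).
- Report fentanyl by arm, as Table 1 does, and note that intraoperative fentanyl in group B may be part of the allocated treatment.
- State the form and coding of the Table 6 models. Label any model with fentanyl as a predictor exploratory and associational.
- Do not call postoperative fentanyl a predictor of the 5-minute score unless it is shown to precede that score.

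The cost is a rerun of the Table 6 models and revised text. No new data are needed.

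### The pain regression gives type of block, an unordered three-arm factor, one verdict at each time and does not say which arms differ, so it cannot by itself support caudal over opioid

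*SAP*

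**What the plan says.** The only statement of the model is in the SAP under Data management: "Linear regression analysis was used to detect the predictors of pain scale". The same paragraph adds "All tests were two-sided" and sets the significance level at 0.05. It does not state how the three arms enter the model, which arm is the reference, or which contrasts are tested.

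The arms are caudal (A, "received general anesthesia with caudal block including 29 patients"), opioid (B, "general anesthesia with an opioid group with a total of 33 participants") and penile block (C, "patients with a penile block 28 patients").

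The Results text on Table 6 names type of block as a predictor at every time. At 5 minutes it stands with intra- and postoperative fentanyl, and at 60 minutes with weight. In between, "the type of block was only the significant predictor of the 10, 20, and 30-minute pain scale". No pair of arms is named, whereas Table 1 has a column of significant pairs for age, sevoflurane and fentanyl.

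On direction, the Results text says that mean pain was much higher in group C and lowest in group A. The protocol's cover letter concludes that a caudal block can give longer analgesia, and names no comparator.

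**The concern.** The title asks how caudal compares with other methods. With two other methods there are two questions: caudal against opioid, and caudal against penile block. One significance verdict for the whole factor answers neither. It can be significant because one arm stands apart while the other two are alike.

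Coding adds a second, conditional problem. If arm was entered as one number (A=1, B=2, C=3), a linear regression forces the caudal-to-opioid step to equal the opioid-to-penile step. The arms have no natural order that would justify this.

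At stake is what may be concluded about caudal. A significant block effect, printed beside a lowest mean in group A and a conclusion with no comparator, lets a reader credit caudal with an advantage over both alternatives when the evidence may bear on only one.

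**Working it through.** **Inputs** (SAP, Results). Arm sizes are 29, 33 and 28. For group B, "The percentage of severe discomfort in group B in 5, 10, 20, and 30 minutes post-operative was 18.2, 6.1%, 3.0%, and 0.0% respectively". Group C has 82.1%, 25.0%, 21.4% and 3.6% at the same times. For group A the text mentions a single patient at 5, 10 and 20 minutes. I read this as 1 of 29 at each time, and assume 0 of 29 at 30 minutes because no case is mentioned.

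**Reproducing the printed figures.** Count = percentage × n, rounded. B: 6, 2, 1, 0 of 33, which gives back 18.2, 6.1, 3.0 and 0.0%. C: 23, 7, 6, 1 of 28, which gives back 82.1, 25.0, 21.4 and 3.6%. As a check on the arm sizes, Pearson chi-square on the five crying tables gives 0.3445, 0.3755, 0.1995, 0.9122 and 0.4068, against 0.344, 0.375, 0.200, 0.912 and 0.407 in Table 2. No regression coefficient or p-value is in the supplied text to reproduce.

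**The two contrasts of interest.** Difference = x/n in the comparator minus x/n in caudal. At 5 minutes, opioid minus caudal = 6/33 - 1/29 = 18.18% - 3.45% = +14.7 points, and penile minus caudal = 23/28 - 1/29 = 82.14% - 3.45% = +78.7 points. p-values are two-sided Fisher exact tests.

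| Minutes | A | B | C | B - A (points) | p | C - A (points) | p |
|---|---|---|---|---|---|---|---|
| 5 | 1/29 | 6/33 | 23/28 | +14.7 | 0.11 | +78.7 | <0.001 |
| 10 | 1/29 | 2/33 | 7/28 | +2.6 | 1.0 | +21.6 | 0.025 |
| 20 | 1/29 | 1/33 | 6/28 | -0.4 | 1.0 | +18.0 | 0.052 |
| 30 | 0/29 | 0/33 | 1/28 | 0.0 | 1.0 | +3.6 | 0.49 |

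Penile block against the other two arms pooled gives p<0.001, 0.009, 0.010 and 0.31. The three-arm exact test gives p<0.001, 0.030, 0.025 and 0.31. From 5 to 20 minutes the overall difference is significant while caudal and opioid are not distinguished.

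**What the caudal-opioid comparison can exclude.** Newcombe 95% intervals for B minus A are -2.0 to +31.2 points at 5 minutes, -11.8 to +16.5 at 10 and -14.4 to +12.2 at 20. Power at 5 minutes for the observed rates (3.4% against 18.2%) is about 44%.

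**If arm was one numeric code.** I fitted ordinary least squares to the 0/1 severe-discomfort indicator, once with arm as 1/2/3 and once with two indicators.

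| Minutes | One slope, points per step | p | Two indicators, joint p | Equal steps, p |
|---|---|---|---|---|
| 5 | +39.2 | <0.001 | <0.001 | 0.001 |
| 10 | +10.7 | 0.010 | 0.017 | 0.22 |
| 20 | +8.9 | 0.018 | 0.018 | 0.12 |
| 30 | +1.8 | 0.21 | 0.33 | 0.44 |

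The equal-step test is F = (RSS of one slope - RSS of two indicators) / (RSS of two indicators / 87). At 5 minutes this is (11.248 - 9.982) / (9.982 / 87) = 11.03, p=0.001.

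**The case against.** The strongest objection is that the regression table cannot be seen. Table 6 and Figure 3 are not in the supplied text, and one line of prose fits two indicators or a joint factor test as well as a single code. Table 6 may already print arm coefficients. This stands: numeric coding is a possibility, not a finding. If the coefficients are there, the remaining work is the model without fentanyl, the adjustment for multiplicity and the wording.

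Nor does coding change the verdict on block in the stand-in data: it is significant, or not, under both codings at every time. Equal steps are rejected only at 5 minutes. This also stands, and it is why the point rests on the missing contrasts and not on the coding.

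A reader might infer that the authors present the regression as showing caudal to be better than opioid. No sentence says so. The Results text sets severe discomfort in group C against the other two groups, and the cover letter's conclusion does not cite the regression. A reader might equally infer that caudal and opioid were shown to be alike. The interval at 5 minutes and the 44% power do not support that either.

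Finally, severe discomfort is one category of the behavioural score, analysed here without covariates. The regressed outcome is the pain scale, whose means and SDs are not in the text. The figures therefore show where the signal probably lies; they do not re-estimate the regression.

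**Conclusion.** The concern holds in a limited form. The Results text gives one verdict per time for an unordered three-arm factor and does not name the arms that differ. A significant block effect cannot by itself support caudal over opioid. This is more than a missing detail, because the conclusion as printed cannot say which method caudal improves on.

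On the printed counts the signal comes mainly from penile block from 5 to 20 minutes. At 10 and 20 minutes caudal and opioid are almost equal on this measure, though the intervals are wide. At 5 minutes a difference is neither shown nor excluded. At 30 minutes one severe case in total shows nothing, and no 60-minute percentages are in the text.

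This rests on severe discomfort standing in for the pain scale, on one caudal child at each of 5, 10 and 20 minutes, and on none at 30. The equal-step problem at 5 minutes applies only if arm was entered as a single number.

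**What to change.** 1. State in Data management how arm enters the regression. Use two indicator variables with caudal as reference, and refit if arm was coded as one number.
2. Leave intra- and postoperative fentanyl out of the model used for the arm contrasts. It was given after randomisation and differs by arm (Table 1: intraoperative means 9.9, 22.1 and 16.4; postoperative 4.8, 10.5 and 5.2; both p<0.001). Adjusting for it would condition the opioid-minus-caudal contrast on opioid use.
3. At each time, report opioid minus caudal and penile minus caudal on the pain scale with 95% CIs and Holm-adjusted p-values. Say whether Holm covers the two contrasts within a time or all ten (2 contrasts × 5 times).
4. Reword the Results sentence on Table 6 to name the contrast that differs at each time, and give the protocol's caudal conclusion a comparator, limited to what those contrasts support.

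The cost is a rerun on existing data and one degree of freedom relative to a single code, out of 90 children. The conclusion may become narrower: it might hold against penile block only.
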